ostomy support groups. In addition, even where a group is attended, the content is neither systematic, nor based on self-efficacy and skills enhancement, as in our proposed intervention. High levels of consumer satisfaction and outcome evaluations have documented the value of cancer support groups.³⁵ Research conducted on face-to-face support groups has revealed positive outcomes.³⁵ However, this research also reveals variations in rates of participation and attendance. Slevin and colleagues provided evidence that physician and nurse-led support groups were preferred by patients, but at least 20% of those invited did not join the group, and another 20% dropped out before the last session.³⁶ These numbers were approximately the same for Goodwin et al.—66% participated, and 19% dropped³⁷—and by Classen et al.—20% declined to participate and 20% dropped.³⁸ In contrast to the live groups, on-line groups conducted by CancerCare in New York City have had tremendous success recruiting people to virtual telephone groups and having them persist when multiple sessions were conducted.³⁹ Each of the four 1-hour long sessions on “Living With, Through and Beyond Cancer” had more than 3,000 callers. Clearly, participation through tele-communication can be more successful for cancer survivors than attending face-to-face support groups.

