12.0 STATISTICAL CONSIDERATIONS

12.1 General. Aim 1 will be analyzed with linear mixed models for repeated measures. Aim 2 will utilize a variety of sources and methods to enumerate the intervention program and ostomy-related family resources in each study arm.

If a subject misses Session 3 or Session 4 or both, they can make up the missed session(s) with the next 1 or 2 scheduled groups. If they miss both chances to make up the sessions, they

will be asked to do the surveys and will be analyzed as a separate group using an intent-to-treat contrast.

12.2 Aim 1: Using our enhanced telehealth techniques, determine if **patient activation**, self-efficacy, ostomy-related knowledge, and HRQOL will be improved and sustained over time in the online interactive communication Ostomy Self-Management Telehealth program (OSMT) curriculum compared to a UC group.

Under an intent-to-treat approach, change in outcomes will be evaluated longitudinally with linear mixed models, testing the effect of study arm adjusted for potential confounders. Such models evaluate both associations and rates of change, accounting for within-subject correlation. The Primary Outcome will be PAM. Secondary Outcomes include SE, COH-QOL-CRC scales, and Ostomy Knowledge. Post hoc contrasts will evaluate effect of training (baseline to post) and whether effect is sustained after training (6 month post to follow-up). Standard multivariable modeling procedures will be used to select or eliminate potential confounding variables, starting with candidate variables that are biologically plausible or found to be associated with endpoint change scores (baseline vs. follow-up) in bivariate analyses with a p-value of less than 0.20. Potential candidate covariates and confounders include (but are not limited to) CG participation in training sessions, depression (HADS), time since surgery, ostomy type, age, sex, stage, anticipated permanence of ostomy, and pre- or post-surgical radiation or chemotherapy. We will explore potential interaction for plausible effect modifiers, such as gender, or having a CG.

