12.11 Avoidance of Bias. Randomized trials tend not to be vulnerable to confounding, observation, and information bias. We will further control confounding in multiple regression analysis. Selection bias will be avoided by blinding the assessment team to randomized arm prior to assignment. We will also collect demographic and clinical data, as permitted, on non-participating eligible patients for comparison. We do not expect substantial loss to follow up, given the duration of follow up, our reminder systems, and ability for make-up webinars. If we find there is participation bias by limited times, we will vary times offered for the sessions.

12.12 Qualitative Data. We have an open-ended question at the end of the questionnaire in Appendix D – Survivor/Family Use of Ostomy Care: "... Please share with us the **greatest challenge** you have encountered in having an ostomy." As indicated in the proposal, qualitative content will be placed into an Excel file. Using a qualitative, grounded theory approach⁴⁴ and content analysis⁴⁵, all survey responses will be reviewed by at least two of the investigators working independently to create a list of unique topics from the data. Codes for these topics will be assigned and grouped into relational categories. The resulting code book with categories and topics will be reviewed separately by two coders in an attempt to resolve any discrepancies in coding. The codebook will then be shared among the entire Research Team, discussed, and any data discordantly coded will be discussed for refinement and consensus. The resulting content will be used to provide data for manuscripts in the same way it was used in the Research Team's past publications with similar text data.⁴⁶⁻⁵⁰

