12.13 Sample Size and Power. Total potential sample size 240 (up to 120 per arm), to ensure at least 75 per arm completing the study with complete baseline COH-QOL-CRC scaled items, assuming a 15% dropout rate. This will maintain sufficient power for the COH-QOL-CRC scaled items. The larger sample size for the primary endpoints Patient Activation Measure (PAM) and ostomy management self-efficacy (SE) will provide 80% power to detect a 2.75 change in PAM and a 0.50 change in SE, which is not considered excessively powered. Detectable differences based on variances observed from our R21 for PAM and SE, as well as from our R01 for COH-QOL-CRC subscales. We changed two items slightly on the self-efficacy questions to make them ostomy-relevant. Our observed variation for ostomy management SE is consistent with the original form of symptom management SE across different patient samples reported by Lorig's group (SD range 2.1 to 2.4).⁵¹⁻⁵⁷ We will examine the reliability of these items and expect them to have a Cronbach's alpha of ≥ 0.75 . Calculated detectable differences were based on the following assumptions 1) alpha of 0.05, 2) within-subject correlation on repeated measures of 0.60. Estimates are based on repeated measures multivariable modeling, adjusted for baseline,

with two follow-up measurements. Also shown for comparison are two rough indices of clinically important differences. Sufficient research has not been performed on these scales to determine with certainty a minimal clinically-important difference that is anchored on participant self-assessment of health status. An alternative suggested by Sloan⁵⁸ is the empirical rule effect size (ERES) method to judge minimally important differences (MID) in outcome measures. We also present 50% of the observed sample SD, a common rule-of-thumb for clinically meaningful differences.⁵⁹ The table shows that even with substantial shortfall in sample size (down to 65 per group) we still can detect differences below the estimated MID.

Detectable Outcome Differences with 80% Power						
Measure	SD	N= 75	N=70	N=65	ERES⁵⁸	.5 SD⁵⁹
Patient Activation Measure	13	3.4	3.5	3.6	8.0	6.5
Ostomy self-management self-efficacy	2.3	0.60	0.62	0.64	0.80	1.2
COH-QOL-CRC Total	1.6	0.42	0.43	0.45	0.88	0.8
COH-QOL-CRC Physical	1.8	0.47	0.49	0.51	0.88	0.9
COH-QOL-CRC Psychological	1.8	0.47	0.49	0.51	0.88	0.9
COH-QOL-CRC Social	2.1	0.55	0.57	0.59	0.88	1.1
COH-QOL-CRC Spiritual	2.2	0.57	0.59	0.62	0.88	1.1

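### The intent-to-treat PAM comparison relies on an unstated missing-at-random assumption with no dropout sensitivity analysis; at 15% dropout the effect could be overstated by 0% to 18%

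*Protocol*

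**What the plan says.** Protocol 12.2 and the SAP (Aim 1) carry the same sentence on the primary analysis: "Under an intent-to-treat approach, change in outcomes will be evaluated longitudinally with linear mixed models". PAM is the primary outcome. Neither document states a missing-data assumption, an imputation rule for absent participants or a sensitivity analysis for dropout. The missing-item rules in protocol 8.2.9 deal with skipped questions, not with people who return no survey.

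On the expected amount of loss, protocol 12.11 says "We do not expect substantial loss to follow up", citing the length of follow-up, reminders and make-up sessions. Protocol 12.13 sizes the trial "assuming a 15% dropout rate", without splitting that figure by arm or by survey.

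The plan does try to obtain surveys from people who stop attending. Non-respondents are telephoned after 2 weeks (8.2.6). Payment is made per survey time, not per session (7.2.5). The 6-month survey is timed from completion of the interim survey, to allow for delays (8.1). Participants who miss Session 3, Session 4 or both, and also both make-up chances, are still surveyed (8.1 and 12.1). The same two sections then have these participants analysed as a group apart, under an intent-to-treat contrast that is not defined. The SAP does not repeat that rule.

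**The concern.** The question is the effect of being assigned to OSMT rather than usual care (UC), in everyone randomised. A likelihood-based mixed model answers it only if, given the observed data, people with missing surveys would have had the same course as people in their arm who were surveyed. Someone who leaves OSMT and returns no later survey is in effect credited with the course of comparable OSMT participants who did. If leavers keep less of the benefit, the model estimates the effect in those who stayed but reports it under an intent-to-treat label.

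The trial is open and PAM is self-reported, so a link between dropout and response is plausible. Nothing in the plan would tell a reader whether a positive PAM result depends on the missing-at-random assumption.

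The rule for session non-completers adds to this. If they are taken out of the main OSMT contrast, the OSMT course is learned mainly from session completers, and a similar bias can arise even when the non-completers' surveys are in hand.

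**Working it through.** **Inputs.** Dropout 15%, PAM SD 13, correlation 0.60 and two follow-up surveys (protocol 12.13). At up to 120 per arm, 15% is 18 people, leaving 102. The share g of the stayers' benefit that leavers keep, and the split of losses between the two surveys, are not in the documents. They are assumptions and are shown as ranges.

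**The plan's own figure.** The table row reads "Patient Activation Measure 13 3.4 3.5 3.6 8.0 6.5". The detectable difference is (1.96 + 0.84) × 13 × √(2f/n). With f = (1 − 0.60²)/2 = 0.32 this gives 3.36, 3.48 and 3.61 at 75, 70 and 65 per arm, which matches 3.4, 3.5 and 3.6. This f treats the two follow-ups as independent given baseline. The usual factor for a baseline-adjusted mean of two follow-ups, (1 + 0.60)/2 − 0.60² = 0.44, gives 3.95 at 75 per arm. The percentages below do not depend on that choice; 3.4 only sets the scale.

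**All leavers lost before any post-baseline survey.** Let D be the effect in stayers.
- Effect in everyone randomised: D(0.85 + 0.15g). Model estimate: D. Ratio: 1/(0.85 + 0.15g).
- g = 0: 1/0.85 = 1.176, so 18%. With D = 3.4 the true effect is 2.89, a gap of 0.51 points. With D = 2.75 it is 2.34.
- g = 0.5: 1/0.925 = 1.081, so 8%.
- g = 1: 0%.

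**Some leavers return the first survey.** Let e be the share of the OSMT arm lost before the end-of-sessions survey and l the share lost after it, with e + l = 0.15. Assume correlation 0.60 between all three surveys and the same g at both follow-ups.
- End of sessions: m₁ = D(0.85 + l·g)/(1 − e).
- 6 months: m₂ = D − 0.375(D − m₁), where 0.375 = 0.60/(1 + 0.60) is the coefficient of the first follow-up when the second is predicted from baseline and the first.
- Half lost early, g = 0: m₁ = (0.85/0.925)D = 0.919D, and 0.919/0.85 = 1.08. Then m₂ = (1 − 0.375 × 0.081)D = 0.970D, and 0.970/0.85 = 1.14.
- All lost late, g = 0: m₁ = 0.85D, so no bias at end of sessions. Then m₂ = (1 − 0.375 × 0.15)D = 0.944D, and 0.944/0.85 = 1.11.

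| Leavers lost before first survey | Benefit kept | Overstatement, end of sessions | Overstatement, 6 months |
|---|---|---|---|
| All | None | 18% | 18% |
| All | Half | 8% | 8% |
| Half | None | 8% | 14% |
| Half | Half | 4% | about 6.5% |
| None | None | 0% | 11% |
| None | Half | 0% | 5% |
| Any | All | 0% | 0% |

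A simulation of the maximum-likelihood estimate with these inputs agrees. All rows take UC dropout as uninformative.

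**Direction when there is no true effect.** Suppose 15% drop out of OSMT selectively, with an assumed correlation c between staying and the baseline-adjusted PAM residual, and UC dropout is random. The shift is c × 13√0.44 × 0.2331/0.85, where 0.2331 is the normal density at the 15% cut-point. That is 0.47 points at c = 0.2 and 0.71 at c = 0.3, in favour of OSMT. The same pattern in UC alone gives the same shift in UC's favour, and equal patterns in both arms cancel.

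**The case against.** The strongest reply is that the plan separates stopping sessions from stopping surveys, and works to keep the surveys. The telephone calls, the payment per survey and the continued surveying of session non-completers should all reduce the number with no post-baseline PAM. For anyone who returns the first follow-up, the model uses that person's own value. This stands, and it is why 18% is a ceiling. The ceiling is also 0.51 points on 3.4, small beside the plan's important-difference indices of 6.5 and 8.0, though not beside the 2.75 to 3.4 that the trial is sized to detect.

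The attendance models (12.2 and the SAP) and the group-apart contrast also bear on how PAM varies with sessions completed. They are informative, but neither is a missing-data analysis of the arm comparison.

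Four stronger readings are tempting, and the documents do not support them.
- **That 12.11 contradicts 12.13.** An expectation that loss will not be substantial is compatible with a 15% planning allowance.
- **That 20% dropout, and so 25% overstatement, is the realistic figure.** The Background reports that "another 20% dropped out before the last session", but this concerns face-to-face groups and leaving sessions, not unreturned surveys. The text goes on to contrast such groups with remote ones that kept their participants.
- **That bias must favour OSMT because only OSMT has sessions to leave.** UC participants may leave because they are disappointed or not helped, and OSMT participants may leave because they already manage well.
- **That 18% is the expected error.** It needs zero retained benefit and no post-baseline survey from any leaver.

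**Conclusion.** The gap is real. The primary PAM contrast rests on missing at random, neither document says so, and no sensitivity analysis tests it. At the plan's 15% dropout the overstatement of the all-randomised effect lies between 0% and 18%, or at most about 0.5 PAM points on 3.4. This range assumes that leavers keep somewhere between none and all of the stayers' benefit, that 15% applies to the OSMT arm, and that UC dropout is uninformative. If UC dropout is informative as well, the bias can shrink or reverse.

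The rule that sets session non-completers apart is the clearer textual threat to intent-to-treat. It can be read as an extra contrast or as removal from the OSMT arm, and the SAP is silent. It has to be settled first, because these participants are also the best evidence on what happens to PAM in people who stop. None of this invalidates the mixed model as the primary analysis; the plan should be amended before analysis.

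**What to change.** In protocol 12.2 and the SAP:

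1. Keep the mixed model as primary and state that it assumes missing at random.
2. State that all randomised OSMT participants, including those who miss Session 3 or 4 and both make-ups, stay in the OSMT arm for the primary PAM contrast. Make the group-apart analysis supplementary, and carry the rule into the SAP.
3. Add one pre-specified multiple-imputation sensitivity analysis of the PAM arm contrast. Impute OSMT participants who stopped sessions and lack a later PAM from OSMT participants who stopped but returned surveys; attendance is recorded at every session (9.4). If there are too few of these, impute from the UC course. Impute UC from UC. Set the minimum number of donors in advance: with about 18 leavers per arm at most (15% of 120), the fallback may be needed, and it comes close to assuming that no benefit is kept.
4. Report this estimate beside the primary one, and say in the conclusion if the PAM result depends on missing at random. It informs interpretation and is not a second test that must be passed.

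In 12.11, give the 15% planning figure from 12.13 in place of the general statement.

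The cost is a few sentences and one more analysis on data already being collected. The second estimate may be up to about 15% smaller (2.89/3.4 = 0.85).

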4.1 Inclusion of Women and Minorities

This study was designed to include women and minorities, but was not designed to measure differences of intervention effects. The anticipated accrual in the ethnicity/race and sex categories is shown in the table below.

Estimated Final Racial/Ethnic and Gender Enrollment Table

Race	Male (N)	Female (N)	Total (N)
American Indian/Alaska Native	0	0	0
Asian	4	6	10
Black/African-American	19	21	40
Hawaiian/Pacific Islander	0	0	0
White	45	47	92
Multi-race	1	3	4
Ethnicity	Male (N)	Female (N)	Total (N)
Hispanic (Latino/Latina)	8	10	18

Non-Hispanic	63	69	132
--------------	----	----	-----

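### The 80% power claimed for a 2.75 difference in PAM and 0.50 in self-efficacy is not delivered by the design under the plan's own dropout and correlation assumptions.

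*Protocol*

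**What the plan says.** All sample-size text is in Protocol section 12.13; the SAP has none. The enrolment figure is given as "Total potential sample size 240 (up to 120 per arm), to ensure at least 75 per arm completing the study", and the sentence continues "with complete baseline COH-QOL-CRC scaled items, assuming a 15% dropout rate". The 75 therefore carries two conditions: finishing the study, and a complete set of baseline quality-of-life items. No expected rate is given for the second.

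The section then says that the larger sample available for PAM and self-efficacy (SE) "will provide 80% power to detect a 2.75 change in PAM and a 0.50 change in SE". It does not give that sample, or say whether it means enrolled or analysed participants.

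The stated assumptions are alpha 0.05, a within-subject correlation of 0.60, adjustment for baseline, and two follow-up measurements. The table covers 75, 70 and 65 per arm only. PAM (SD 13) is 3.4, 3.5 and 3.6; SE (SD 2.3) is 0.60, 0.62 and 0.64. Section 12.2 and the SAP name PAM as the primary outcome.

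**The concern.** The two headline differences lie outside the table, and no n is attached to them. A reader would take them to hold for the sample that the plan expects to analyse. If they do not, the power statement for the primary outcome is too favourable.

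A second question is whether the table itself follows from the listed assumptions. If it uses a smaller variance than a correlation of 0.60 implies, every detectable difference in the section is too small. In that case, attaching an n to 2.75 and 0.50 would not repair the statement.

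**Working it through.** **Inputs (section 12.13).** 120 per arm; 15% dropout; 75 completers; alpha 0.05 (two-sided assumed); power 80%; correlation 0.60; two follow-ups; SD 13 (PAM) and 2.3 (SE). Allocation is 1:1 (section 7.2.2).

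**Enrolment.** 75 / 0.85 = 88.2, so 89 per arm and 178 in total. In the other direction, 120 × 0.85 = 102 per arm.

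**Formula.** Detectable difference = (1.960 + 0.842) × SD × √(2f/n), where f is the variance factor for the mean of two follow-ups adjusted for baseline:

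f = (1 + r)/2 − ρ²

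Here r is the correlation between the two follow-ups and ρ is the correlation of each with baseline.

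**Reproducing the table.** f = (1 − 0.36)/2 = 0.32 gives, at 75, 70 and 65 per arm:

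- PAM: 3.36, 3.48, 3.61 (table 3.4, 3.5, 3.6)
- SE: 0.595, 0.616, 0.639 (table 0.60, 0.62, 0.64)

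With a noncentral t in place of the normal, every PAM, SE and COH-QOL-CRC Total cell agrees to the printed digits. So do the Social and Spiritual rows. Among the other two rows, Physical and Psychological, only the cells at 65 differ, by 0.01.

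**What 0.32 implies.** Solving (1 + r)/2 − 0.36 = 0.32 gives r = 0.36 = 0.60². The two follow-ups are then correlated only through baseline. With 0.60 between all pairs, f = 0.80 − 0.36 = 0.44.

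**Detectable differences, and power for 2.75 (PAM) and 0.50 (SE).**

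| n per arm | f | PAM | Power for 2.75 | SE | Power for 0.50 |
|---|---|---|---|---|---|
| 75 | 0.32 | 3.4 | 63% | 0.60 | 65% |
| 102 | 0.32 | 2.9 | 76% | 0.51 | 78% |
| 120 | 0.32 | 2.7 | 83% | 0.47 | 85% |
| 75 | 0.44 | 4.0 | 50% | 0.70 | 52% |
| 102 | 0.44 | 3.4 | 62% | 0.60 | 65% |
| 120 | 0.44 | 3.1 | 70% | 0.55 | 72% |

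**A check on the table's scale that needs no factor.** Scaling the printed values by √(75/n) gives 3.4 × √(75/102) = 2.92 for PAM and 0.60 × √(75/102) = 0.514 for SE. Allowing for rounding, 2.75 needs about 112 to 115 analysed per arm and 0.50 about 107 to 109. Neither 102 nor 120 gives the quoted pair.

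**Against the protocol's benchmarks (f = 0.44, 102 per arm).** PAM 6.5: 13 × √(0.88/102) = 1.207 and 6.5/1.207 = 5.38, so power exceeds 99.9%. SE 0.80: 2.3 × √(0.88/102) = 0.214 and 0.80/0.214 = 3.74, so power is about 96%. Even at 65 per arm, SE is about 0.75, still below 0.80.

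**The case against.** The strongest defence is that 2.75 and 0.50 were never tied to completers. The analysis is an intent-to-treat mixed model that can use a participant with one follow-up, and people who miss their make-up sessions are still asked for surveys. The effective n may therefore lie between 102 and 120, and on the table's scale 120 meets both figures. On that scale the SE shortfall at 102 is also marginal. This answers the dropout part of the point only. With the stated correlation applied to both follow-ups, full data on 120 per arm still gives about 70% and 72%.

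It can also be said that 0.60 was meant only for the correlation with baseline. That is possible. The protocol then leaves the follow-up correlation unstated, and the table implies 0.36, so that each follow-up agrees less with the other than with baseline. That needs a reason.

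Three stronger readings are tempting, and the documents do not support them.

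- A reader might call 240 an arithmetic error, since 75 completers at 15% dropout need only 178. But 240 is a ceiling, it satisfies a floor of 75, and the floor has the second condition of complete baseline items.
- A reader might infer that 27 of 102 completers (26%) are expected to lack usable quality-of-life data. That rate comes from treating the ceiling as the plan and the floor as the expectation. The protocol states no such rate.
- A reader might cite the section 4.1 table ("Estimated Final Racial/Ethnic and Gender Enrollment Table"), which totals 146 by race and 150 by ethnicity. Those totals do not enter the power calculation.

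**Conclusion.** The power statement for PAM and SE is wrong as written. At the plan's own dropout rate and on the table's own scale, the miss is modest for PAM (about 2.9, power 76%) and marginal for SE (0.51, power 78%). Under the correlation that the section states, it is larger: about 3.4 and 0.60 at 102 per arm, with power of 62% and 65% for the quoted differences. No sample within the ceiling of 120 per arm reaches 80%.

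This assumes a two-sided test, equal allocation, a constant SD, an arm effect averaged over both follow-ups and, for n = 102, no follow-up data from dropouts. The factor 0.32 is inferred from the table's values; the protocol does not give its formula.

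It would go too far to conclude that the trial is underpowered for differences that matter. PAM stays well below its 6.5 to 8.0 benchmarks, and SE stays below 0.80. The enrolment figure is incompletely explained, but it is not shown to be wrong.

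**What to change.** Do not enrol more. In section 12.13:

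1. Recompute the whole detectable-difference table and the PAM and SE sentence with one stated variance formula. With 0.60 throughout (factor 0.44), the 75-per-arm column becomes about 4.0 for PAM and 0.70 for SE. Change the table and the sentence together: the new values at 102 equal those now printed at 75, so changing the sentence alone would show the same differences at both sizes.
2. Name the n, and quote PAM and SE at 102 per arm: about 3.4 and 0.60.
3. If the sponsor keeps 0.32, state and justify the follow-up correlation of 0.36 and quote about 2.9 and 0.51 at 102.
4. State the sponsor's own expected rate of complete baseline COH-QOL-CRC, so that the step from 120 enrolled to 75 can be followed. The back-solved 26% should not be written in.

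The cost is a text and table revision with less favourable stated differences. Design, enrolment and analysis do not change.

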**Statistical Analysis Plan**

## Statistical Analysis Plan

**General.** Aim 1 will be analyzed with linear mixed models for repeated measures. Aim 2 will utilize a variety of sources and methods to enumerate the intervention program and ostomy-related family resources in each study arm.

**Aim 1:** Using our enhanced telehealth techniques, determine if **patient activation**, self-efficacy, ostomy-related knowledge, and HRQOL will be improved and sustained over time in the online interactive communication Ostomy Self-Management Telehealth program (OSMT) curriculum compared to a UC group.

Under an intent-to-treat approach, change in outcomes will be evaluated longitudinally with linear mixed models, testing the effect of study arm adjusted for potential confounders. Such models evaluate both associations and rates of change, accounting for within-subject correlation. The Primary Outcome will be PAM. Secondary Outcomes include SE, COH-QOL-CRC scales, and Ostomy Knowledge. Post hoc contrasts will evaluate effect of training (baseline to post) and whether effect is sustained after training (6 month post to follow-up). Standard multivariable modeling procedures will be used to select or eliminate potential confounding variables, starting with candidate variables that are biologically plausible or found to be associated with endpoint change scores (baseline vs. follow-up) in bivariate analyses with a p-value of less than 0.20. Potential candidate covariates and confounders include (but are not limited to) CG participation in training sessions, depression (HADS), time since surgery, ostomy type, age, sex, stage, anticipated permanence of ostomy, and pre- or post-surgical radiation or chemotherapy. We will explore potential interaction for plausible effect modifiers, such as gender, or having a CG.

The COH QOL-CRC assesses ostomy burden and care abilities, including time taken to perform daily ostomy care, comfort with ostomy care, comfort with diet, adjustment of diet for ostomy, appetite, clothing and other problems with ostomy placement. We will also measure clinically related outcomes, including medical attention for problems with bowel, bladder, or ostomy. Changes in these responses will be compared between treatment groups with linear mixed models, chi-square tests or t-tests, as appropriate.

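### The detectable-difference table does not follow from its only stated correlation, 0.60, and the 80% power claim for PAM 2.75 and SE 0.50 gives no sample size

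*Protocol*

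**What the plan says.** Protocol section 12.13 (Sample Size and Power) lists alpha of 0.05, without saying one- or two-sided, and a "within-subject correlation on repeated measures of 0.60". On the model it says "Estimates are based on repeated measures multivariable modeling, adjusted for baseline", with two follow-up measurements. The table gives differences detectable with 80% power at 75, 70 and 65 per group for PAM (SD 13), self-efficacy (SE, SD 2.3) and five COH-QOL-CRC scores (SD 1.6 to 2.2). For PAM these are 3.4, 3.5 and 3.6.

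The enrolment of 240, up to 120 per arm, is explained as securing "at least 75 per arm completing the study with complete baseline COH-QOL-CRC scaled items, assuming a 15% dropout rate". For PAM and SE the larger sample "will provide 80% power to detect a 2.75 change in PAM and a 0.50 change in SE", "which is not considered excessively powered". No N is attached to those two figures. The section concludes that with a shortfall to 65 per group "we still can detect differences below the estimated MID".

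PAM is the primary outcome (Protocol section 12.2 and the SAP). The SAP has no sample-size section.

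**The concern.** There are three assessments: baseline, end of sessions and six months. A single correlation quoted for repeated measures is most naturally read as applying to all three pairs. On that reading the table cannot be obtained from its listed assumptions, and every printed difference is too small for the power in the heading.

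If the PAM result is null, readers will use these figures to judge what the trial could have missed. For a true PAM difference of 3.4 at 75 per arm, the chance of missing it would be about 33% instead of 20%. The 2.75/0.50 sentence rests on the same calculation and cannot be checked without an N.

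**Working it through.** **Inputs from section 12.13.** SDs as tabulated; alpha 0.05, taken as two-sided; power 80%; n = 75, 70 or 65 per arm; correlation 0.60; baseline adjustment; two follow-ups. Dropout 15% and a maximum of 120 per arm are used only in step 4.

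**Assumption.** The powered contrast is the baseline-adjusted arm difference averaged over the two follow-ups. The protocol does not name the contrast.

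**Formula.** With r0 the baseline-to-follow-up correlation and r12 the correlation between the follow-ups, the variance factor is f = (1 + r12)/2 − r0². The detectable difference is approximately (1.960 + 0.842) × SD × √(2f/n). Results below use the noncentral t with 2n − 2 degrees of freedom.

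**Step 1: reproduce the printed table.** Take f = (1 − 0.60²)/2 = 0.32. For PAM at 75, the normal approximation is 2.802 × 13 × √(0.64/75) = 3.36. The noncentral t gives 3.39, 3.51 and 3.64 at 75, 70 and 65, against 3.4, 3.5 and 3.6 printed. In all, 19 of 21 entries match to the printed digit. The two misses are Physical and Psychological at 65 (0.504 against 0.51).

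**Step 2: apply 0.60 to every pair.** f = (1 + 0.60)/2 − 0.60² = 0.80 − 0.36 = 0.44. No entry matches. One-sided alpha does not rescue it: PAM becomes 3.52, 3.64 and 3.78, and again no entry matches. The ratio of detectable differences is √(0.44/0.32) = 1.173.

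| Measure | Printed, N = 75/70/65 | 0.60 on every pair |
|---|---|---|
| PAM | 3.4/3.5/3.6 | 4.0/4.1/4.3 |
| SE | 0.60/0.62/0.64 | 0.70/0.73/0.76 |
| COH-QOL-CRC Total | 0.42/0.43/0.45 | 0.49/0.51/0.53 |
| Physical, Psychological | 0.47/0.49/0.51 | 0.55/0.57/0.59 |
| Social | 0.55/0.57/0.59 | 0.64/0.66/0.69 |
| Spiritual | 0.57/0.59/0.62 | 0.67/0.70/0.72 |

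At f = 0.44 the printed entries have 65.6% to 67.6% power; PAM 3.4 at 75 per arm has 67.0%.

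**Step 3: what could give 0.32.** The table fixes only f. Several inputs lead there, none of them stated:
- r0 = 0.60 and r12 = 0.36, which means the follow-ups are independent given baseline. With 0.60 throughout, their correlation given baseline would be (0.60 − 0.36)/(1 − 0.36) = 0.375.
- 0.74 on every pair, from (1 + r)/2 − r² = 0.32.
- r12 = 0.60 with r0 = √(0.80 − 0.32) = 0.69.
- 0.60 on every pair, with further covariates removing 1 − 0.32/0.44 = 27% of the remaining variance.

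**Step 4: PAM 2.75 and SE 0.50.** Completers are 120 × 0.85 = 102 per arm.

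| Factor | Power at 120, no dropout (PAM/SE) | Power at 102 completers | Completers per arm for 80% |
|---|---|---|---|
| 0.32 | 82%/84% | 76%/78% | 114/108 |
| 0.44 | 69%/72% | 62%/64% | 156/148 |

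Differences detectable with 80% power are 2.9/0.51 at 102 with f = 0.32. With f = 0.44 they are 3.4/0.60 at 102 and 3.1/0.55 at 120.

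**Step 5: the below-MID statement at 65 per arm, f = 0.44.** PAM is 4.3 against 6.5. The COH-QOL-CRC scores are 0.53 to 0.72 against 0.80 to 0.88. SE is 0.76 against 0.80. Each comparison uses the smaller of the two tabulated indices.

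**The case against.** The strongest reply is that the protocol never says 0.60 holds for every pair, and that it describes multivariable modelling. Section 12.2 and the SAP list many candidate covariates, so a factor of 0.32 may have been intended. This stands as far as it goes: the 17% and the 67% are conditional on reading 0.60 as common to all pairs. But no second correlation and no covariate R-squared is given, so the table cannot be checked from what is written.

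A reader might infer from the close match that the planners assumed 0.36 between the follow-ups. That is one inference among several; the documents establish only a factor near 0.32.

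It is also fair that 75 per arm is the reduced case for PAM, since the protocol gives PAM and SE the larger sample. At 102 completers PAM 3.4 has 80% power even with a factor of 0.44. That helps the design, but the table still heads the 75-per-arm entries with 80% power, and the larger-sample claim is for 2.75, not 3.4.

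A reader might further infer that the trial is too small. The documents do not support this. Enrolment is justified by COH-QOL-CRC completers, the 2.75/0.50 sentence only defends the larger sample against being excessive, and the below-MID statement survives.

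**Conclusion.** The point holds as a mismatch between stated assumptions and stated figures. With 0.60 on every pair, two-sided alpha and the contrast averaged over the follow-ups, detectable differences are about 17% larger than printed and power at the printed values is about 66% to 68%. It cannot be said that the printed values are wrong in themselves, because unstated inputs could justify them.

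The 2.75/0.50 claim needs correction on either basis. Even with the table's own factor it requires 114 (PAM) and 108 (SE) completers per arm, more than the 102 that remain from 120 after the protocol's own 15% dropout.

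The one place where the protocol's conclusion becomes tight is SE at 65 per arm: the margin below the MID index falls from 0.16 (0.80 − 0.64) to about 0.04 (0.80 − 0.76).

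**What to change.** In section 12.13, state that alpha is two-sided, which contrast the power refers to, the correlation for each pair of the three assessments, any covariate R-squared used, and the N behind 2.75/0.50. Then take one of two routes.

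1. **If 0.60 applies to every pair:** replace the table with the right-hand column in step 2, and restate 2.75/0.50 as 3.4 in PAM and 0.60 in SE at 102 completers per arm (3.1 and 0.55 at 120 with no dropout).
2. **If the sponsor's data support the inputs behind 0.32:** state those inputs and keep the table. Either restate 2.75/0.50 as 2.9 and 0.51 at 102 completers per arm, or say that 2.75/0.50 applies at 120 per arm with no dropout.

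The named contrast should be the one the planners used. Sections 12.2 and the SAP test the effect of study arm and keep separate contrasts for training effect and sustained effect, so the power text should not settle that choice by default.

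The cost is a few sentences and, on the first route, one table with less favourable figures. Enrolment, visits and analysis stay as they are.
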